Effects of Pioglitazone on Stress Reactivity and Alcohol Craving

NCT03860753

Version Date: 05/08/2019

ABSTRACT

Alcohol use disorder (AUD) is associated with significant negative health, social, and economic costs. Alcohol activates the hypothalamic-pituitary-adrenocortical (HPA)-axis, and stress can increase the reward value of drinking. Continued excessive drinking results in behavioral changes marked by increased compulsive drinking, stress reactivity, and neuro-inflammation⁸. FDA-approved pharmacotherapies for AUD (e.g., naltrexone, acamprosate, disulfiram) are effective in less than a third of treated individuals⁹. *Importantly, none of the currently approved medications for AUD directly address stress reactivity, underscoring the need to develop novel pharmacotherapies targeting stress-related processes associated with AUD.*

A promising pharmacological target for addressing AUD and stress reactivity is the family of peroxisome proliferator-activated receptors (PPARs), proteins that act as ligand-activated transcription factors that exhibit both anti-inflammatory and neuro-protective responses in the brain¹⁰. A growing number of pre-clinical models have shown promising effects of PPAR agonists on drug-related outcomes¹¹. For example, the PPAR γ agonist pioglitazone *1) significantly reduced free-access alcohol consumption; and 2) attenuated alcohol consumption and withdrawal symptoms following stress exposure in rats bred to highly prefer alcohol*^{12,13}. An important innovation of the current study will be to translate these results for the first time to humans with AUD.

The primary purpose of the current proposal is to obtain preliminary data to increase the likelihood of funding for a future NIH grant, while balancing the feasibility of completing the current proposal. To that end, we will utilize a within-subject, repeated measures design to assess the feasibility of administering pioglitazone for four weeks to non-treatment and treatment-seeking individuals with AUD and elevated levels of stress/anxiety (**N=20**). Participants will undergo pre- and post-treatment human laboratory assessment of stress-reactivity and stress-induced alcohol craving. During treatment, changes in alcohol use, stress/anxiety, and alcohol craving will be assessed in the natural environment. The study design features 1) rigorous monitoring of medication compliance (Medication Event Monitoring System (MEMs)) and alcohol use (urinary ethyl glucuronide (ETG)); 2) biological assessment of stress reactivity (salivary cortisol, blood pressure, and heart rate); and 3) a multi-dimensional assessment of stress-induced alcohol craving incorporating both traditional measures of alcohol craving in addition to relatively novel behavioral economic measures (delay discounting, alcohol demand). Taking these measures together, we hope to present a robust and comprehensive characterization of pioglitazone on alcohol use, stress reactivity, and stress-induced alcohol craving.

SPECIFIC AIMS

Specific Aim 1: To assess pre- to post-treatment reductions in stress reactivity (self-report, salivary cortisol, heart rate, blood pressure) and stress-induced alcohol craving (self-report, alcohol demand) in the human laboratory setting.

Hypothesis 1: *We will observe pre- to post- treatment reductions in stress reactivity and stress-induced alcohol craving.*

Specific Aim 2: To assess changes in alcohol drinking (drinks per day, heavy drinking days), stress/anxiety (PSS, HAMA, PCL-5), and alcohol craving (PACS, delay discounting, alcohol demand) during treatment in the natural environmental setting.

Hypothesis 2: *We will observe decreased alcohol drinking, stress/anxiety, and alcohol craving over the course of treatment.*

There is increasing attention and evidence supporting the potential role of the PPAR γ system as a novel target in the treatment of AUD. From a translational perspective, this study is timely and likely to advance our understanding of stress as a mechanism of action of pioglitazone effects.

IRB NUMBER: HSC-MS-18-0922

BACKGROUND AND RATIONALE

Public Health Impact of AUD. AUD is 1) the 4th leading cause of death in the US (~88,000 deaths/year), decreasing lifespan by approximately 30 years; 2) a tremendous economic burden on society (~\$249 billion/year); and 3) associated with a host of short- and long-term negative consequences including violence, legal problems, morbidity, and family problems^{14–16}.

AUD and the Central Role of Stress. Persistent excessive drinking is a chronic stressor that 1) shifts brain systems beyond normal homeostatic limits into a state of allostasis; 2) which in turn alters physiological and brain motivational systems central for regulating alcohol use; and 3) has negative impact on autoimmune and inflammatory responses that can in turn influence alcohol use^{17–21}. Whereas initial drinking is influenced by the positive reinforcing effects of alcohol and impulsivity, continued drinking adopts compulsive characteristics maintained increasingly by negative reinforcement (e.g., alcohol withdrawal symptoms, stress-related anxiety, alcohol craving) as well as decreased stress-resiliency and cognitive deficits from neuro-inflammatory damage^{17,22,23}. Despite the profound negative impact of stress on AUD, *none of currently approved medications for AUD directly target stress or stress-related consequences associated with AUD*.

Novelty and Promise of the PPAR System. PPARs are proteins that act as ligand-activated transcription factors, which is central to their anti-inflammatory actions²⁴. Pre-clinical studies highlight the potential of PPAR agonists on various aspects of drug use (e.g., discrimination, self-administration, reinstatement, sensitization) for several drugs of abuse including alcohol¹¹. In human studies, expression of PPAR has been shown to be altered among individuals with AUD in genome-wide association studies (GWAS) ^{25,26} studies. In a recent study by our group, post hoc analyses revealed significantly decreased alcohol use among individuals with concurrent cocaine use disorder (CUD) and AUD receiving the PPAR_γ agonist pioglitazone, compared to placebo, in a study assessing cocaine craving and white matter integrity.²⁷.

Currently, only the PPAR gamma (PPAR_γ) isoform can be targeted in humans. PPAR_γ is highly expressed in a number of brain regions associated with drug reward²⁸ and stress response^{12,13}. Activation of PPAR_γ mediates neuroprotective responses against inflammatory damage, which can attenuate drug affects^{29–32}. The PPAR_γ agonist Pioglitazone (Actos) is FDA-approved for the treatment of diabetes and metabolic disorders. In preclinical studies, pioglitazone protects against 1) alcohol-induced neuronal and cognitive damage in a model of binge-drinking³³; and 2) neuro-inflammation and neurodevelopmental toxicity in a model of fetal alcohol spectrum disorder³⁴. Directly relevant to the current study, *pioglitazone 1) significantly reduced alcohol drinking in rats; and 2) attenuated stress-induced alcohol drinking and alcohol withdrawal symptoms in rats bred to highly prefer alcohol*^{12,13}.

Multi-Dimensional Assessment of Alcohol-Induced Craving. Self-report measures of drug craving are ubiquitous and often serves as a proxy of motivation to consume drug but have limitations that have likely resulted in equivocal results in human laboratory studies³⁵. Behavioral economic measures (i.e., delay discounting, alcohol demand) may help mitigate these issues and are both closely associated with drug use and directly tied to a broader framework of drug addiction. Delay discounting is a relatively stable, trait-like measure that assesses the decrease in value of a reward as a function to delay of its receipt, and also serves as a measure of impulsivity. Delay discounting has an extensive literature revealing associations with virtually every aspect of drug use including initiation, severity, and relapse risk^{36–38}. Alcohol demand assesses how much alcohol an individual is willing to consume as a function of increasing price, serving as 1) a robust characterization of the reward value of alcohol and therefore craving; and 2) a proxy of compulsive drug use (i.e., consuming alcohol despite increasing aversive consequences). Drug demand can be easily and quickly assessed through purchasing tasks, which have very strong reliability, predictive validity, and are sensitive to state-dependent changes in demand under conditions of withdrawal, cue exposure, environmental stressors,

and predict alcohol treatment response³⁹⁻⁴². Delay discounting and alcohol demand are poorly correlated with each other, supporting a multi-dimensional model in which these measures represent distinct aspects of motivation to use alcohol⁴²⁻⁴⁸. In the current proposal, we will assess changes in both delay discounting and alcohol demand over Study Weeks 0 to 4 and alcohol demand will be used to assess state-dependent changes during the human laboratory stress-reactivity assessment.

METHODS

Research team. The research team will consist of [name] (PI) and a number of collaborators from UTHealth and Brown University. [name] (PI) is an experienced addiction researcher and an expert in assessing behavioral economic measures in addiction research, which is pertinent to the current project. Drs. [name] (CNRA Medical Director) and [name] (Addictions Psychiatrist) will provide medical guidance and ensure participant safety over the course of the study. [name] is Professor and Vice Chair for Research and directs the Behavioral Laboratory at the CNRA with expertise in medication development trials as well as alcohol studies. [name] is a biostatistician and data scientist with expertise in experimental design and statistical modeling, including the type of generalized linear modeling that will be utilized by the present research. From Brown University, [name] (Co-I) is serving as a consultant on this project and is an expert in stress and alcohol research¹⁻⁷. Additionally, our group has a history of collaborating with the Laboratory of Biomarkers located in the BBSB for analyzing biological samples, such as salivary cortisol in the current protocol. We will work with [name] to ensure that samples are collected and analyzed appropriately.

Overall study design. We will utilize a within-subject, repeated measures design. Participants will receive pioglitazone or placebo for four weeks. A summary of the study timeline, procedures, and assessments is shown in the following Table.

Table 1. Outline of Study Timeline, Procedures, and Assessments

Study Week Procedures and Assessments	0	1	2	3	4
Consent and Baseline Screening SCID, ASI, KMSK, TLFB, CIWAA, AUDIT	X				
Receive Study Medication (Pioglitazone or Placebo) Assess Medication Compliance and Adverse Events	X	X	X	X	X
Human Laboratory Procedures (Specific Aim 1) Stress-Reactivity Assessment (Salivary Cortisol, HR, BP, Craving) Alcohol Demand, Alcohol Ladder	X				X
Human Laboratory Procedures (Specific Aim 1) Stress-Reactivity Assessment (Salivary Cortisol, HR, BP, Craving) Alcohol Demand, Alcohol Ladder	X				X
Natural Environment Procedures (Specific Aim 2) Alcohol Use and Craving (Self-Report, BrAC, ETG, PACS) Stress and Anxiety (HAM-A, PSS, BDI-II, PCL-5) Delay Discounting, Alcohol Demand	X	X	X	X	X
Natural Environment Procedures (Specific Aim 2) Alcohol Use and Craving (Self-Report, BrAC, ETG, PACS) Stress and Anxiety (HAM-A, PSS, BDI-II, PCL-5) Delay Discounting, Alcohol Demand	X	X	X	X	X

SCID - Structured Clinical Interview for DSM-5; **ASI** - Addiction Severity Index⁴⁹; **KMSK** - Kreek-McHugh-Schluger-Kellogg scale⁵⁰; **TLFB** - Timeline Followback⁵¹; **CIWAA** - Clinical Institute Withdrawal Assessment for Alcohol⁵²; **AUDIT** - Alcohol Use Identification Test⁵³; **BrAC** - Breath Alcohol Concentration; **ETG** - Ethyl Glucuronide; **PACS** - Pennsylvania Alcohol Craving Scale⁵⁴; **HR** - Heart Rate; **BP** - Blood Pressure; **HAM-A** - Hamilton Anxiety Rating Scale⁵⁵; **PSS** - Perceived Stress Scale⁵⁶; **PCL-5** - PTSD Checklist for DSM-5; **BDI-II** - Beck Depression Inventory - II.

Participants, Recruitment, and Setting. Participants (**N=20**) will consist of non-treatment and treatment-seeking individuals diagnosed with AUD (DSM-5) between 21 to 40 years old and fluent in English; past month excessive alcohol use (>7 drinks/week for women, >14 drinks/week for men, >3 drinks/occasion for women>4 drinks/occasion for men)¹⁴; baseline HAM-A or PSS Score indicative of mild to moderate anxiety (score 8 to 23) or moderate stress (score 14 to 26), respectively; and increase in alcohol craving following the

baseline stress reactivity assessment. Individuals will be excluded for exhibiting severe scores on the HAM-A, PSS, BDI-II, or PTSD checklist (PCL-5) at the discretion of the admitting physician ([name]); physical dependence on alcohol; greater than mild substance use disorder on drugs other than alcohol, nicotine, and marijuana; contraindications for taking pioglitazone; medical conditions contraindicating pioglitazone pharmacotherapy or taking contraindicated medications; be pregnant, nursing, or planning on becoming pregnant during the course of the study; have any other illness, condition, or use of medications, which in the opinion of the PI and/or admitting physician would preclude safe and/or successful completion of the study. Recruitment strategies will include local advertising in print media, public service announcements on radio, and referrals to CNRA in the Houston metropolitan area.

Baseline Screening. Participants will receive a comprehensive medical and psychiatric evaluation including: a medical-history questionnaire, physical examination, laboratory chemistries (e.g., blood chemistry screen, complete blood count, urinalysis and urine pregnancy test), and ECG. Clinicians will conduct the **SCID**, the **ASI ASI**⁴⁹, the **KMSK**⁵⁰ assessment of lifetime substance use interview, and **TLFB**⁵¹. Alcohol dependence will be assessed using the SCID and the **CIWAA**⁵².

Alcohol-Related Measures. Assessment of alcohol use will include self-report (**TLFB**), **BrAC** (Alco-Sensor FST, Intoximeters, Inc., Saint Louis, MO). Severity of alcohol use will be assessed using the **AUDIT**⁵³. **Motivation to quit** will be assessed using the Alcohol Ladder questionnaire. **Alcohol craving** will be assessed using a 5-item questionnaire⁵⁷. ETG will be assessed using dipcards with a 300 ng/ml cutoff. ETG dipcards show good agreement with traditional immunoassays⁵⁸⁻⁶⁰.

Behavioral Economic Measures. Alcohol demand will be assessed via the **Brief Assessment of Alcohol Demand** (BAAD)⁴², a 3-item questionnaire measuring the three most common indices of alcohol demand. **Delay discounting** will be assessed for both money and alcohol using a computerized task at weekly clinic visits developed by [name] (PI)^{61,62,71,63-70}.

Stress and Anxiety Measures. Stress and anxiety levels will be assessed using the **HAM-A**⁵⁵, **PSS**⁵⁶, **BDI-II**, and the **PCL-5**. Established norms will be used for the HAM-A and PSS to assess mild to moderate stress and anxiety and screen out for cases of severe stress and anxiety.

Stress Reactivity Measures. HR and BP will be assessed using standard laboratory equipment. Saliva samples will be collected in swabs using the Cortisol-Salivette® system (Sarstedt) and measured using the Cortisol ELISA Kit (Enzo Life Sciences), per manufacture instructions.

Study Medication. Pioglitazone (Actos®, Takeda Pharmaceuticals U.S.A., Inc.) is FDA-approved for the treatment of diabetes mellitus type 2; has anti-inflammatory, neuroprotective, antioxidative, and anti-excitotoxic properties⁷²; and extensive research has shown it to be safe in human patient populations^{73,74}. The medication schedule is based on previous work from our group showing that a daily dose of 45mg was associated with acceptable levels of tolerability, safety, and compliance in a study assessing the effects of pioglitazone on individuals with CUD and AUD²⁷. Our pilot trial used a conservative 2-week dose titration schedule (i.e., Week 1: 15 mg/d; Week 2: 30 mg/d), with no adverse effects reported or observed. For the current trial we will follow recommended adult initial dosing at 30 mg/d to reach maintenance dose of 45 mg/d by week 2, which is within standard titration parameters as per the investigator's brochure. Thorough screening of all subjects including history and physical examination, serum chemistry and hematology, EKG, urinalysis and Urine Drug Screen as well as structured psychiatric interviews will be completed on all subjects. Exclusion criteria include subjects at greatest risk of side effects of pioglitazone, including those with congestive heart failure, significant liver disease, edema, and diabetes, as well as risks of alcohol use (pregnant

women). Monitoring of weight to capture potential fluid retention will occur at each visit along with an adverse event assessment to include assessment for edema. Blood will be drawn at the end of the study for liver function testing. Female subjects must agree to use an effective barrier method of birth control and urine pregnancy tests will be performed at each visit to minimize risk of pregnancy.

Medication Compliance. One week supplies of the study medication will be dispensed with a Medication Event Monitoring System (MEMS) cap to record the number of bottle openings and date/time of each opening. Riboflavin will be added to medication capsules and urine ultraviolet fluorescent tests will be conducted at weekly clinic visits to assess compliance. Participants will receive \$10 at each clinic visit in which results from self-report, MEMS, and riboflavin are all consistent with medication compliance.

Human Laboratory Procedures (Specific Aim 1). On Study Weeks 0 and 4, participants will engage in the cold-pressor task (CPT). The CPT is widely used as a stress-inducer in human laboratory studies and elicits moderate activation of the sympathetic nervous system and limited activation of the HPA-axis, which are two major stress systems in the body⁷⁵⁻⁷⁸. HPA-axis activation during the CPT can be increased by incorporating a social evaluative component. Specifically, a study member of the opposite sex of the study participant will dress in a white labcoat and be physically present during the CPT. Additionally, participants will be videotaped and informed that their facial expressions will be assessed during the CPT. The addition of the social component during the CPT has been demonstrated to selectively activate the HPA-axis and significantly increase salivary cortisol levels⁷⁷. During the CPT, participants will submerge their dominant arm in an ice-water bath for up to 2 minutes. Stress levels will be assessed using subjective and physiological measures HR, BP, and salivary cortisol consistent with previous studies from our group^{79,80}. Alcohol craving will be assessed using a 4-item questionnaire⁵⁷.

Table 2. Time Course for Assessing Stress-Induced Relapse Risk

Time (pm)	Study Procedures
3:00	Assess Craving, BAAD, Stress, Cortisol, HR, BP
3:15	Cold Pressor Task
3:20	Assess Craving, BAAD, Stress, HR, BP
3:45	Assess Craving, BAAD, Stress, Cortisol, HR, BP

Natural Environment Procedures (Specific Aim 2). At Study Week 0, all participants will receive a pamphlet copy of the “Rethinking Drinking: Alcohol and Your Health” providing research-based information related to alcohol use (RethinkingDrinking.niaaa.nih.gov). Research staff will go over the pamphlet’s information with the participant at the initial visit and subsequent visits as necessary. At each study visit, participants will receive study medication for the week and assessed for adverse events and medication compliance. At each visit, participants will also be assessed for recent alcohol use (self-report, ETG, BrAC), alcohol craving (PACS), and stress/anxiety (HAM-A, PSS). At the end of the study, participants will be referred to local alcohol treatment services as needed.

Participant Payment & Compensation. Participants will receive be able to receive \$300 for completing the study (\$50 for completing baseline screening; \$25 for each visit (\$100); \$25 for stress reactivity assessments (\$50); and \$100 completion bonus). Additionally, participants will potentially receive \$10/week (up to \$40) for demonstrating medication compliance. Participants will also receive parking/bus fare compensation at each visit worth \$5.

DATA ANALYSIS PLAN

General Data Analytic Strategy. Analyses will proceed in parallel using frequentist and Bayesian statistical inference. Frequentist analyses will examine relationships between predictors and outcomes using traditional measures of effect size and statistical significance (i.e., regression coefficients, standard errors,

confidence intervals, and p -values), while Bayesian analyses will measure uncertainty in model parameter estimates via posterior distributions and directly evaluate the probability of the alternative hypothesis.

Specific Aim 1: assess pre- to post-treatment reductions in stress reactivity (self-report, salivary cortisol, heart rate, blood pressure) and stress-induced alcohol craving (self-report, alcohol demand) in the human laboratory setting.

Hypothesis 1: We will observe pre- to post- treatment reductions in stress reactivity and stress-induced alcohol craving. Generalized linear mixed modeling will be used to evaluate each outcome as a function of time (pre-test and post-test) in unique models.

Specific Aim 2: Demonstrate reduced alcohol drinking (drinks per day, heavy drinking days), stress/anxiety (PSS, HAMA, PCL-5), and alcohol craving (PACS, delay discounting, alcohol demand) during treatment in the natural environmental setting.

Hypothesis 2: We will observe decreased alcohol drinking, stress/anxiety, and alcohol craving over the course of treatment. Generalized linear mixed modeling will be used to evaluate each outcome as a function of time in unique models. Alcohol consumption will be modeled via drinks per drinking day, such that the number of positive drinking episodes a participant experienced in a week will be included as a count outcome (i.e., Poisson-distributed) and the number of drinking days in a week will be controlled for as an off-set covariate.

Power/Sample Size Considerations. The frequentist framework using null hypothesis statistical testing can provide some understanding of changes over time for each outcome. However, in evaluating a small within-subjects pilot trial of $N = 20$ participants, Bayesian statistical inference provides a superior framework for deriving evidence regarding the magnitude and direction of change over time for each model. The posterior probability of each effect would then be useful to inform effect sizes for power calculations and/or prior distributions in future research. As due diligence, however, a conventional frequentist power analysis follows. For the current proposal, power estimates are calculated using G*Power 3.1.9.2 and focus on reduction in alcohol consumption. Assuming alpha = 0.05 (one-tailed), an average baseline rate of 10.5 drinks/week across all participants (averaged between 14 and 7 drinks/week for male and female participants, respectively), a sample size of $N = 20$ participants provides 80% power to detect a 20% decrease in alcohol consumption over five weeks.

REFERENCES

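### The methods name a placebo, but every planned model contains time alone, so no result can be attributed to pioglitazone

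*Combined protocol and SAP*

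**What the plan says.** The document gives two descriptions of who receives what.

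- **Drug or placebo.** Overall study design: "Participants will receive pioglitazone or placebo for four weeks". The medication row of Table 1 agrees: "Receive Study Medication (Pioglitazone or Placebo".
- **Drug only.** Abstract: "we will utilize a within-subject, repeated measures design to assess the feasibility of administering pioglitazone for four weeks", in a sample of 20, with no mention of placebo. The Study Medication paragraph also describes only pioglitazone.

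The analysis follows the second description.

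- Hypothesis 1: "Generalized linear mixed modeling will be used to evaluate each outcome as a function of time (pre-test and post-test) in unique models".
- Hypothesis 2: "Generalized linear mixed modeling will be used to evaluate each outcome as a function of time in unique models". The only further term is an offset for drinking days in the consumption model.
- The power paragraph treats all 20 participants as one group. It uses one-tailed alpha 0.05 and a baseline of 10.5 drinks/week, and claims 80% power for a 20% fall over five weeks.

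Randomisation, allocation ratio, blinding and crossover are stated nowhere. The Abstract nevertheless hopes to characterise pioglitazone's effect on drinking, stress reactivity and craving. The power paragraph proposes to use the results for future power calculations or priors.

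**The concern.** A reader cannot tell whether the trial has one arm or two, and the planned models do not isolate a drug effect in either case.

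**If placebo is given**, a time-only model averages drug and placebo participants. Its coefficient is the mean change in the mixture. A real drug effect is diluted, and a change shared by both groups is counted as if it were the treatment result.

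**If placebo is not given**, the time coefficient has several competing explanations:

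- Everyone receives the Rethinking Drinking pamphlet, which staff go over "with the participant at the initial visit and subsequent visits as necessary".
- Drinking, stress and medication-taking are monitored weekly.
- Entry requires excessive drinking in the past month and a HAM-A or PSS score in a raised band. It also requires a rise in craving at the baseline stress test. That craving response is itself an Aim 1 outcome, so participants are selected on the Week 0 value against which Week 4 is compared. Some regression to the mean is therefore expected.
- The cold-pressor task is repeated, so habituation can lower the second response.

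At stake is the trial's stated purpose: the effects handed to the next grant would be time effects presented as information about pioglitazone.

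**Working it through.** **1. Side-by-side reading.** Placebo appears in the design sentence and in Table 1. It is absent from the Abstract's design statement, both hypotheses, both model statements and the power paragraph. "We will utilize a within-subject, repeated measures design" cannot be read as a crossover, because Table 1 has a single run from Week 0 to Week 4 with no second period.

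**2. Reproducing the stated 80%.** The plan names G*Power but not the test, and gives no SD, dispersion or within-subject correlation. The closest match found is a Poisson log-linear trend in one group of 20. It has five weekly points (t = 0, 0.25, 0.5, 0.75, 1), a rate falling from 10.5 to 8.4, and no overdispersion.

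- Effect: b = −ln 0.8 = 0.2231
- Null SE: √[1/(20 × 10.5 × 0.625)] = 0.0873, where 0.625 = Σ(t − 0.5)²
- SE under the alternative, from the Poisson information matrix: 0.0923
- Power = Φ[(0.2231 − 1.645 × 0.0873)/0.0923] = Φ(0.86) = 80.6%
- Wald version: Φ(0.2231/0.0923 − 1.645) = Φ(0.77) = 78.0%

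The stated figure is therefore consistent with one group followed over time. This shows one workable reading and need not be the calculation actually run.

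**3. Inert drug, with everyone's drinking falling.** The documents give no background decline, so a range is shown for the same time test:

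| Non-specific fall | Probability that the time effect is significant |
|---|---|
| 5% | 14–15% |
| 10% | 32–33% |
| 15% | 56–58% |
| 20% | 78–81% |

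**4. Two arms, effect on drug only.** Assume 1:1 allocation, a 20% fall on drug and none on placebo. The pooled end rate is (8.4 + 10.5)/2 = 9.45, a 10% fall, so b = −ln 0.9 = 0.1054.

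- Planned pooled time test: Φ[(0.1054 − 1.645 × 0.0873)/0.0896] = Φ(−0.43) = 33%; Wald 32%.
- Arm-by-time contrast, 10 per arm: variance = 0.01705 (drug) + 0.01524 (placebo) = 0.03229, SE 0.1797. Wald power = Φ(0.2231/0.1797 − 1.645) = Φ(−0.40) = 34%; with the null variance, 36%.
- For 80% power on that contrast: 39–41 per arm (78–82 in total), one-sided.

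**5. A second model as a check.** Compare one baseline week with four on-treatment weeks, using Poisson counts.

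- Time test, 20% fall: variance = (1/10.5 + 1/(10.5 × 0.8 × 4))/20 = 0.00625, SE 0.0791. Power = Φ(0.2231/0.0791 − 1.645) = 88%.
- Pooled 10% fall: variance 0.00608, SE 0.0780, power 38%.
- Arm contrast, 10 per arm: variance = (1/10.5 + 1/33.6)/10 + (1/10.5 + 1/42)/10 = 0.0244, SE 0.156, power 41%. If the variance is 2 or 3 times the mean, power is 26% or 21%.

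This model gives 88% where the plan states 80%, so step 4 is closer to the plan's basis. Both models point the same way.

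**The case against.** The strongest reply is that this is a single-arm pilot with stray placebo wording. Most of the text supports that: the within-subject label, the pre-to-post hypotheses, a medication paragraph with no placebo product, and a power statement for one group of 20. On that reading no arms are pooled, and the hypotheses already speak of change over time. The lack of a control is then an open limitation of a small feasibility study. The plan sets no formal success criterion and does not expressly label the effects it carries forward as pioglitazone effects.

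Part of this stands. Pooling and dilution apply only if a placebo arm exists, and the text does not settle that. The entry bands for anxiety and stress have upper limits, so regression to the mean is better supported for drinking and for the baseline craving rise than for stress scores. The power figures rest on assumed allocation and dispersion. They concern weekly drinks, whereas the Aim 2 consumption model is a count with a drinking-days offset.

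The central point survives. Placebo is named in two places in current text, and nothing in the analysis accommodates it. Pilot status excuses low power but not an undefined comparison. On the single-arm reading the Abstract's aim of characterising pioglitazone is still out of reach, because change over time is the only quantity estimated.

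**Conclusion.** The concern holds, and the plan is wrong as written. The design statements contradict each other, and under either reading the planned models estimate change over time and not the effect of pioglitazone. The contradiction and the missing treatment term are plain in the text and rest on no assumption.

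The size is illustrative. On the plan's own power claim, a 20% non-specific fall with an inert drug would be significant about 80% of the time. If there are two arms of 10 and only the drug lowers drinking by 20%, the planned test has about 32–33% power under the model that best matches the stated 80%, and 38% under the alternative. The arm-by-time contrast has 34–36% and 41% respectively, falling to 21% if the variance is three times the mean. These figures assume 1:1 allocation, no change on placebo and, except where stated, no overdispersion.

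**What to change.** Reconcile the Abstract, Overall study design, Table 1 and Data Analysis Plan so that they describe one design.

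- **If placebo is given:** state randomised allocation, its ratio, and blinding. Add arm and arm-by-time to every Aim 1 and Aim 2 model, with a common baseline mean or the Week 0 value as a covariate. Make that contrast the reported estimate in both the frequentist and Bayesian analyses. Replace the 80% statement with power or expected precision for the contrast at N = 20.
- **If placebo is not given:** remove it from the design sentence and Table 1. Describe the hypotheses and conclusions as uncontrolled change over time, and name the pamphlet, monitoring, selection at entry and repeat testing as alternative explanations. Do not use the time effects as pioglitazone effect sizes or priors for later studies.

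The cost is protocol and SAP wording plus, in the two-arm case, the treatment terms in each model. No extra participants or procedures are needed to make the analysis correct. The two-arm version must accept that N = 20 yields an imprecise estimate: 80% one-sided power would need about 78–82 participants under the assumptions above.
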